## **4.2 Exclusion Criteria**

- 4.2.1 Patients not undergoing radioembolization to the liver
- 4.2.2 Women of childbearing potential (WOCBP) and men who refuse to comply with appropriate contraception as described in section 4.4 below.
- 4.2.2 Women who are either pregnant or breast feeding. Refer to section 4.4 for further detail.

## **4.3 Inclusion of Women and Minorities**

Men and women, regardless of race, ethnic group or sexual orientation are eligible for this study.

## **4.4 Pregnancy**

The effects of this clinical trial on the developing human fetus are unknown. For this reason and because radiation as well as other non-therapeutic agents used in this trial are known to be teratogenic, women of child-bearing potential (WOCBP) and men must agree to use adequate contraception (hormonal or barrier method of birth control; abstinence) prior to study entry, for the duration of treatment, and for at least 3 months after the last radiographic evaluation. Should a woman become pregnant or suspect she is pregnant while participating in this study, she must inform her treating physician immediately.

Prior to study enrollment, WOCBP must be advised of the importance of avoiding pregnancy during trial participation and the potential risk factors for an unintentional pregnancy. In addition, men enrolled on this study should understand the risks to any sexual partner of childbearing potential.

All WOCBP must have a negative pregnancy test no more than 72 hours prior to registration. If the pregnancy test is positive, the patient must not receive the visit 1 scan and must not be enrolled in the study.

WOCBP is defined as follows: Any female who has experienced menarche and who has not undergone successful surgical sterilization (hysterectomy, bilateral tubal ligation, or a bilateral oophorectomy) or is not postmenopausal (defined as amenorrhea  $\geq$  12 consecutive months, or women on hormone replacement therapy (HRT) with documented plasma follicle-stimulating hormone (FSH) level  $>$  35 mIU/ml). Even women who are using oral, implanted, or injectable contraceptive hormones or mechanical products (diaphragm, condoms, spermicides) to prevent pregnancy or practicing abstinence or where partner is sterile (e.g. vasectomy), are considered to be WOCBP.

## **4.5 Patient Registration Procedure**

Patients will be consented at the time when the decision to pursue radioembolization is made. No protocol-specific workup will take place prior to obtaining informed

consent. However, at this time it will be determined that the patient has had a complete staging workup within the last 4 weeks including:

- Diagnostic imaging of the abdomen utilizing either CT with contrast, MRI, or PET/CT
- Complete metabolic panel (CMP)
- Complete blood count (CBC)
- Coagulation studies (PT, INR)

Eligible patients will be entered on study centrally by the Fox Chase Cancer Center QA Coordinator or their designee. Following registration, participants must begin protocol related treatments and evaluations within 14 days of registration. If a participant does not receive protocol therapy following registration, the participant will be recorded as withdrawn from study and will be replaced. The QA Coordinator must be notified of cancellations and withdraws as soon as possible.

Participants may be registered from 9:00 am to 5:00 pm excluding holidays and weekends by calling the QA Coordinator at [contact]. The site's investigator or designee will then fax the completed registration form, entire, complete and signed informed consent document and HIPAA authorization documents and the completed eligibility checklist to [contact]. The QA Coordinator or designee will notify the site's investigator or their designee by email when participant registration is confirmed and the sequence number has been assigned. Participants must be registered and have received a sequence number assigned by the QA Coordinator prior to the initiation of treatment.

Exceptions to the current registration policies will not be permitted.

## **5.0 Study Procedures**

### **Pretreatment Visit**

A 3 Phase Liver CT simulation must be performed before Visit 1, Day 0 (The treatment Initiation Day). This simulation may occur before or after the staging angiogram, coil embolization, Tc-99m MAA injection, and planar and SPECT imaging of the participant's liver.

### **Visit 1 (Day 0)**

Visit 1 will take place after the pretreatment visits, and will be referred to as Day 0, the day of radioembolization. Visit 1 will include the following procedures:

- Radioembolization as per standard clinical protocol
- PET-CT performed just after the radioembolization in order to measure Yttrium-90 activity for in-patient dose reconstruction
- Subset of patients will get contrast CT

### **Visit 2 (Day 1)**

Visit 2 will take place on Day 1, and will be pursued in only a subset of patients. This will include only a PET-CT for the purposes of determining the stability of microsphere

placement. The Visit 2, Day 1 PET-CT should be scheduled 24 hours +/- 3 hours after the Visit 1, Day 0 post-treatment PET-CT.

### **Follow-up Visits**

Participants will be followed for 5 years or until death, whichever comes first. Follow-up visits will be scheduled at 1 week, 1 month, 3 months, and then every 3 months for one year, every 6 months for 1 year and then annually for 3 years or death whichever comes first

### **Additional Radioembolization Treatments**

As a part of standard of care, many patients will require a second radioembolization.

Patients requiring a second radioembolization treatment will be scanned additionally at Visit 1 (Day 0) and Visit 2 (Day 1) after the second treatment.

Visit 2 of the second radioembolization will take place on Day 1, and will be pursued in only a subset of patients. This will include only a PET-CT for the purposes of determining the stability of microsphere placement. The Visit 2, Day 1 PET-CT should be scheduled 24 hours +/- 3 hours after the Visit 1, Day 0 post-treatment PET-CT.

In these cases the 1 month follow up visit may be conducted on the day of the second treatment.

Follow up visits may be conducted by any investigator and will include the following studies:

- CBC and CMP will be drawn at each follow-up visit
- Beginning at the 3-month visit, each visit should be accompanied by tumor imaging to evaluate local control. The modality of tumor imaging will be at the discretion of the investigator, but it is encouraged to use the same modality consistently over time.

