## **1.0 Introduction**

### **1.1 Abstract**

This protocol for human research study is conducted according to US and international standards of Good Clinical Practice (International Conference on Harmonization (ICH) Guidelines) and applicable government regulations (e.g. Title 45, Part 46 Code of Federal Regulations).

The development of radioembolization with microspheres represents a significant advance in the treatment of patients with metastatic disease to the liver. [1,2] This technique uses semi-empirical formulas for dose calculation that rely on body surface area or crude volumes as the determinants of dose. Moreover, dose is assumed to be uniformly distributed throughout the treated volume. Although the efficacy of treatment and limited side effects are evidence of high intratumoral doses with minimal radiation to normal liver, there have been few attempts to quantify the actual doses delivered. Knowledge of these doses may allow more accurate determination of the effect of dose on response, improved algorithms for prescription of the safest and most effective dose for each patient, and safer integration of additional treatment to the area with either microspheres or external beam radiation. Therefore, we are proposing a new technique to better characterize the dose deposition of radioactive microspheres. The research plan will be based on the recent publication of positron emission from Yttrium 90 (Y-90), which can be utilized to image sphere distribution on a positron emission tomography (PET) scanner, without the administration of additional radiolabeled tracer. Three dimensional dose distributions will be generated and fused onto the CT data of patients to display doses to tumors and normal tissues.

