## 2.0 Objectives

### 2.1 Primary Objective

- To determine the relationship between radiation dose to 70% of the tumor volume as determined by post-treatment PET-CT and local control at 6 months.

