## 8.0 Statistical Considerations

In this study, we will evaluate the dosages received by tumors and surrounding tissue using PET-CT data. The primary objective is to determine the relationship between radiation dose to 70% of the tumor volume and local control at 6 months. We will conduct this analysis at the tumor level, as different tumors may receive different doses of radiation, and may have different progression statuses at 6 months. We will use standard summary measures such as means, medians, ranges, and standard deviations to characterize the dosages received by tumor and other tissue. We will use percentages and frequency tables to evaluate other characteristics such as tumor histology, number of liver tumors per patient, and volume of liver tumors.

We will determine the relationship between radiation dose and local control at 6 months using regression models with Generalized Estimating Equations (GEE) to account for within-patient correlation. We will use logistic regression to adjust for potentially confounding factors such as tumor volume, primary histology, and SIR-Spheres versus Therasphere intervention. We will also determine the relationship between radiation dose to healthy tissue, and side effects such as fatigue, nausea, pain and elevated liver function tests. Each

side effect will be characterized as present or absent, and we will test the relationship between radiation dose to the relevant type of healthy tissue and each side effect. For example, we will look at the relationship between dose to the normal liver and elevation of liver function tests.

In further secondary analyses, we will explore the relationship between the distribution of activity measured by PET-CT, and the distribution predicted by T-99m labeled MAA. This can be translated into predicted dose. We will calculate differences between PET-CT and MAA doses, and present the data graphically. We will use the method proposed by Bland & Altman (2007) to assess the agreement between the two methods. Finally, in a subset of patients, we will explore the change in dose measured by PET-CT scan between day 0 and day 1. The dose at day 1 will be adjusted to account for the decay of the yttrium-90 using  $A=A_0e^{-(0.693t/T_{1/2})}$ . Observed changes in dose may be due to microsphere migration, and our main interest is to look for a systematic change in dose received based on this migration.

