#### Sample size considerations

We will power our study to detect a 10 Gy difference in mean radiation doses between tumors with local control and 6 months vs those which progressed. Based on preliminary data, we expect that the standard deviation of doses will be 12Gy, and that approximately 60% of tumors will retain local control at 6 months. We will use a two-sided test with type I error of 0.05. In preliminary data, within-patient correlation was 0.6-0.7, and we saw an average of 2 tumors per patient. We therefore will enroll 43 patients in this study to have approximately 80% power to detect a difference of 10 Gy.

It is anticipated that 10 patients will be recruited for Day 1 PET-CT studies. This number of patients would be expected to detect a difference in the range of 12-20 Gy (Day 0 – Decay-adjusted day 1). Although we may not get a significant result, the point estimates may give an indication of whether the microspheres are moving. This level of certainty is felt to be appropriate for an exploratory aim.

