### 9.1 Data Reporting

The FCCC Study Monitor will request case report form submission upon resolution of outstanding queries. Participating sites are responsible to respond to queries prior to the next scheduled monitoring visit. Participating sites are responsible for submitting case report forms to the QA Specialist / Study Monitor within two weeks of request.

The QA Coordinator is responsible for compiling and submitting data to the study PI and statistician on an ongoing basis for monitoring as described in the data safety monitoring plan and reporting to the Extramural Data and Safety Monitoring Committee.

All patient information will be stored on an electronic Microsoft Office Excel Spreadsheet on a drive accessible only to the study team members for the purpose of entering, reviewing and analyzing data. Any paper records, such as case report files, produced will be stored in locked file cabinets with limited access.

The CTO Regulatory Coordinator is responsible for distributing and tracking review of all IND Action Letters, Safety Reports, study specific Serious Adverse Events

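### Nothing in the plan keeps whoever scores 6-month local control from knowing the tumour's reconstructed dose, so the primary dose-response association is open to assessment bias

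*Combined protocol and SAP*

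**What the plan says.** Section 2.1 states the main question of the study: "To determine the relationship between radiation dose to 70% of the tumor volume as determined by post-treatment PET-CT and local control at 6 months". Section 8.0 makes the tumour the unit of analysis ("We will conduct this analysis at the tumor level") and fits the relationship "using regression models with Generalized Estimating Equations (GEE) to account for within-patient correlation". The study is powered on this comparison: "We will power our study to detect a 10 Gy difference in mean radiation doses between tumors with local control".

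The exposure comes from the PET-CT done just after radioembolization on Day 0 (Section 5.0, Visit 1). Section 1.1 describes the output: "Three dimensional dose distributions will be generated and fused onto the CT data of patients to display doses to tumors and normal tissues".

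The outcome comes months later. Under Additional Radioembolization Treatments in Section 5.0, "Follow up visits may be conducted by any investigator and will include the following studies". The list that follows asks for tumour imaging from the 3-month visit to evaluate local control, with the modality left to the investigator. The documents do not define local control, name a response criterion, say who reads the images, or mention masking or independent review.

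On data handling, Section 9.1 states: "All patient information will be stored on an electronic Microsoft Office Excel Spreadsheet on a drive accessible only to the study team members". The same section has data compiled for the study PI and statistician on an ongoing basis. It does not separate dose data from outcome data.

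**The concern.** The exposure is known well before the outcome is judged, and the judgement is loosely specified. The study also sets out to show that delivered dose explains response, so the likely direction of an assessor's expectation is clear: borderline high-dose tumours would tend to be called controlled and borderline low-dose tumours progressed.

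Such error depends on the variable under test, so it is not noise that dilutes the association. It pushes the association away from the null. GEE handles within-patient correlation and the planned covariates handle confounding. Neither corrects an outcome that was scored in the light of the exposure.

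**Working it through.** **Inputs from Sample size considerations (Section 8.0).** Design difference 10 Gy; dose SD 12 Gy ("we expect that the standard deviation of doses will be 12Gy"); 60% of tumours controlled; two-sided alpha 0.05; within-patient correlation 0.6-0.7; average 2 tumours per patient; 43 patients.

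**Assumptions not in the documents.** Dose is normally distributed and has no true effect on control. A share q of progressed tumours above the median dose is scored controlled, and the same share of controlled tumours below it is scored progressed. The range shown is q = 0 to 30%.

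**Step 1: the plan's own figure.** Independent tumours needed = (SD × (1.960 + 0.842) / difference)² / (0.6 × 0.4) = (12 × 2.802 / 10)² / 0.24 = 47.1 by the normal approximation, or 50 with the t distribution. With 2 tumours per patient and correlation 0.7 the design effect is 1.7, so 50 × 1.7 / 2 = 42.5, or 43 patients. Those 43 patients (86 tumours, effective 86 / 1.7 = 50.6) give 81.2% power with the t distribution. The stated 43 patients and roughly 80% power reproduce.

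**Step 2: shift caused by dose-aware scoring.** Scored control above the median is a = 0.6 + 0.4q; below it, b = 0.6(1 − q). The mean dose of each half lies 12 × √(2/π) = 9.57 Gy from the centre. The spurious difference, controlled minus progressed, is 9.57 × [(a − b)/(a + b) + (a − b)/(2 − a − b)].

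- q = 10%: a = 0.64, b = 0.54. Odds ratio (0.64/0.36)/(0.54/0.46) = 1.51. Difference 9.57 × (0.10/1.18 + 0.10/0.82) = 1.98 Gy.
- q = 20%: a = 0.68, b = 0.48. Odds ratio (0.68/0.32)/(0.48/0.52) = 2.30. Difference 9.57 × (0.20/1.16 + 0.20/0.84) = 3.93 Gy.
- q = 30%: a = 0.72, b = 0.42. Difference 9.57 × (0.30/1.14 + 0.30/0.86) = 5.86 Gy.

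**Step 3: false-positive rate.** Two methods were used. The first is a t-test on the effective sample size, 86/1.7 to 86/1.6. The second simulates 43 patients with 2 tumours each, correlation 0.65 in both dose and outcome, and a logistic model with cluster-robust variance (4,000 runs per setting).

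| q | Spurious difference, simulated | Type I error, t approximation | Type I error, simulated |
|---|---|---|---|
| 0 | 0 Gy | 5% (nominal) | 4.7% |
| 5% | 0.9 Gy | 5.9-6.0% | 5.1% |
| 10% | 2.0 Gy | 8.7-9.0% | 9.7% |
| 15% | 3.0 Gy | not run | 16.0% |
| 20% | 3.9 Gy | 20-21% | 24.2% |
| 30% | 5.9 Gy | 39-41% | 48.3% |

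With outcome correlation lowered to 0.3 or 0, the simulated rates are 10.0% and 10.3% at q = 10%, and 26.8% and 27.6% at q = 20% (2,000 runs each). Across methods, q = 20% therefore gives 20-28%.

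**The case against.** A reader might infer that the protocol lets any investigator score local control with the dose map in view. The documents do not say that. The sentence in Section 5.0 concerns who conducts visits, not who reads images. Section 1.1 describes the technique and does not route dose maps to whoever reads follow-up scans. Section 9.1 limits file access to the team but does not say that scorers use the file. What the text supports is narrower: nothing prevents a scorer from knowing the dose.

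A reader might also infer that withholding the dose file would remove the bias. It would not. Under Appendix II the Day 0 PET-CT is done partly to verify where the spheres lodged, so an investigator who saw that scan has some idea which tumours took up activity. That knowledge is partial. Section 1.2 says the prescription is total activity without a calculation of delivered dose, and dose to 70% of each tumour exists only after the reconstruction in Section 1.2.1. Withholding that output therefore does mask the exposure variable itself.

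Nor can it be claimed that masking needs no extra staff. The documents do not describe who reads images, and a rule barring anyone who had seen the dose from scoring could require a second reader.

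Two further objections stand. The misscoring rate is assumed, and at 5% the simulated error rate is close to nominal. The symmetric flip around the study median is also stylised, because a scorer during accrual would not know that median. Finally, the missing definition of local control is a separate gap that masking does not fill.

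**Conclusion.** The point holds in this form: the powered primary question links tumour dose to a judged outcome, and the plan has no step that separates the two. If scoring were influenced by dose, the association could be created or inflated, and the planned model would not correct it.

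The size is conditional. Under the stated assumptions the false-positive rate stays at about 5% for misscoring up to 5%, roughly doubles at 10%, reaches 20-28% at 20% and up to 48% at 30%. The spurious difference of about 4 Gy at 20% is over a third of the 10 Gy the study is designed to detect. The documents do not show that dose-aware scoring will happen, or how often. The case for acting is that the safeguard is cheap and that masking, once lost, cannot be restored without re-reading the images.

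**What to change.** In Sections 5.0 and 9.1, state that:

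- each tumour's 6-month status is entered and locked before that patient's reconstructed dose is linked to it or released to whoever scores it;
- dose results are held in a separate access-restricted file until that lock;
- where the scorer has seen the dose earlier for clinical reasons, the score is recorded as unmasked, and the primary analysis is repeated without those tumours as a sensitivity analysis. This avoids requiring another reader.

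The cost is a second file, a lock step and a masked/unmasked flag on the scoring record, and dose-response data cannot be reviewed informally before 6 months. The sensitivity analysis will have fewer tumours and so less precision. The change reduces the bias but does not remove it, because the scorer may have seen the Day 0 PET-CT. No sample size input changes: 43 patients and power of about 81% stand.

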## 6.0 Study Calendar

	Registration Visit	Pre treatment Visit(s)	Visit 1 / Day 0	Visit 2/ Day 1	Follow up
Informed consent & HIPAA A	X				
Medical history	X				
Symptom Guided Physical exam G	X				X
ECOG Performance Status	X				X
CBC w/diff, plts B	X				X
Serum chemistry B	X				X
EKG (as indicated)	X				
β-HCG	X E				
Coagulation Studies B	X	X			
3 Phase Liver CT Simulation		X			
Staging Angiogram		X			
Coil Embolization		X			
Tc-99m (approx 5mCi) MAA Injection		X			
Planar and SPECT Imaging of Liver		X			
Adverse Event Assessment			X	X	X H
PET-CT C,D			X	X	
Tumor Imaging F	X				X I

A: Must be completed less than 28 days prior to registration and prior to any protocol specific tests or procedures.  B: CBC and CMP will be drawn at each follow-up visit, Coagulation studies include PT and INR. Coagulation studies must be performed for eligibility however results will not exclude patient participation.  C: Visit 1, Day 0 post treatment PET CT and contrast CT for subset of participants, Day 1 PET CT.  D: 24 hours +/- 3 hours after Day 0  E: See Section 4.4 for more information – Must be negative within 72 hours of first treatment related procedure or scan  F: Repeat imaging is encouraged to be the same modality (PET-CT, MRI, or contrast CT) as that in baseline study.  G: Physical exam with investigator where he/she reviews symptoms with the participant and addresses any issues that are identified by the participant. This is not the same as a complete physical exam, intentionally.  H: Record only AE's possibly, probably, or definitely related to the visit 2 / day 1 PET/CT scan. Possibly, probably or definitely related AE's must be followed until resolution or 30 days after visit 2.  I: Follow up tumor imaging begins with the month 3 follow up visit.
					

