## 7.0 Adverse Events

For purposes of this clinical trial record only AE's possibly, probably, or definitely related to the visit 1 and visit 2 PET/CT scans. Possibly, probably or definitely related AE's must be followed until resolution or 30 days after visit 2 whichever comes first.

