## **7.2 Recording and Reporting Responsibilities of the participating investigative sites and the sponsor**

### 7.2.1 Participating investigative site recording responsibilities:

These are the directions to be utilized by the site's investigator (sub-investigator) and/or study team at the participating site.

1. Upon identification of an AE or SAE, that is possibly, probably or definitely related to the investigational PET CT scans performed, the site investigator will utilize the above definitions to properly classify the event. Each category listed above must be recorded for each event.
2. Any AE or SAE that is possibly, probably or definitely related to the investigational PET CT scans performed, will be recorded in the "AE case report forms" (CRF) and in progress reports with details about the grade and attribution of each episode, action taken with respect to the study drug, and the patient's outcome will be recorded in the CRF. All events that are possibly, probably or definitely related to the investigational PET CT scans performed, will be recorded on case report forms for the duration of the study until they resolve.
3. All SAEs that are possibly, probably or definitely related to the investigational PET CT scans performed, will be recorded on the FDA

MedWatch form 3500a or other sponsor-provided SAE report form. After submitting the initial report it may be necessary to submit follow up reports to the Study Monitor, Sponsor and /or the FDA should the event require further investigation.

7.2.2 Investigative site reporting responsibilities:

1. The investigator/ site is responsible to report all SAEs that are possibly, probably or definitely related to the investigational PET CT scans performed, to the Study Monitor within 24 hours of becoming aware of the event.
2. Each investigator is responsible to report all AEs/SAEs that are possibly, probably or definitely related to the investigational PET CT scans performed; to their local IRB following guidelines set by that IRB. Fox Chase Cancer Center Quality Assurance (QA) reserves the right to request an event be reported to the IRB at their discretion. Copies of events reviewed by the IRB must be sent via fax to the Regulatory Coordinator at [contact].
3. Any investigator who is in doubt of whether a particular AE needs to be reported is directed to call the Study Monitor for confirmation from the PI.

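### Study Calendar footnote H limits follow-up adverse event recording to the Day 1 scan, while Sections 7.0 and 7.2.1 also cover the Day 0 scan

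*Combined protocol and SAP*

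**What the plan says.** The Study Calendar marks Adverse Event Assessment at Visit 1, Visit 2 and follow-up. Only the follow-up mark carries footnote H: "Record only AE's possibly, probably, or definitely related to the visit 2 / day 1 PET/CT scan".

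Section 7.0 sets the scope for the whole trial and includes the Day 0 scan: "record only AE's possibly, probably, or definitely related to the visit 1 and visit 2 PET/CT scans". Section 7.2.1, item 2, addressed to the sites, has no visit limit at all: "Any AE or SAE that is possibly, probably or definitely related to the investigational PET CT scans performed, will be recorded in the" CRF.

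The Day 0 scan is listed without a subset restriction in Section 5.0, Visit 1: "PET-CT performed just after the radioembolization in order to measure Yttrium-90 activity for in-patient dose reconstruction". Section 5.0 limits Visit 2 to a subset, which the sample size paragraph of Section 8.0 puts at an anticipated 10 patients.

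The rules on how long an event is followed also differ. Section 7.0 says that related events "must be followed until resolution or 30 days after visit 2 whichever comes first". Footnote H uses the same 30-day reference to Visit 2. Section 7.2.1 says that events "will be recorded on case report forms for the duration of the study until they resolve".

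**The concern.** All three places tell sites which adverse events to record, and they give different answers. The available text has no rule on which prevails. Section 7.2 and Section 9.1 provide for participating sites, so different sites could apply different rules.

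A site working from the calendar would leave off the CRF an event judged at least possibly related to the Day 0 scan but first noticed at the 1-week visit or later. A site working from Section 7.0 or 7.2.1 would record it. Under Section 7.0, scan-related events are the only adverse events this trial records, so the scope at follow-up matters to the completeness of that record. Section 9.1 has trial data compiled and passed on for continuing monitoring, and non-serious events missing from the CRF could be missing there too.

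**Working it through.** The plan states no figure for scan-related events, so there is none to reproduce. The check compares the rules and then makes one count.

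**1. Scope of each rule**

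| Place | Scans whose related events are recorded | Applies at |
|---|---|---|
| Section 6.0, footnote H | Visit 2 / Day 1 only | Follow-up |
| Section 6.0, marks without a footnote | No limit in the calendar | Visit 1, Visit 2 |
| Section 7.0 | Visit 1 and Visit 2 | Whole trial |
| Section 7.2.1 | All investigational PET-CT scans performed | Whole trial |

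**2. Footnote H taken literally at a follow-up visit**

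- Patient with no Visit 2: there is no Day 1 scan to which an event could be related, so nothing is recordable.
- Patient with a Visit 2: events related to the Day 1 scan are recordable; events related to the Day 0 scan are not.

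The exclusion of Day 0 scan-related events first found at follow-up therefore does not depend on whether a patient has a Visit 2.

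**3. Count**

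Inputs: 43 patients (Section 3.0) and 10 anticipated Day 1 patients (Section 8.0, sample size).

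- No Visit 2: 43 − 10 = 33; 33/43 = 76.7%.
- Day 0 PET-CT planned: 43/43 = 100%.

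The 33 is approximate. The 10 is an expectation, and Section 5.0 provides for a Day 1 scan after a second radioembolization in a subset, which could lower the number with no Visit 2.

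**4. Where a delayed finding would surface**

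After Day 0, the calendar schedules blood counts and chemistry at follow-up visits only, and the first of these is at 1 week. Section 7.1.1 counts an abnormal laboratory result as an adverse event. A subset receives intravenous contrast CT with the Day 0 PET-CT (Section 3.0; Section 6.0, footnote C; Appendix II). A chemistry change thought possibly related to that contrast would first be seen in scheduled tests at a visit under footnote H, and the unrestricted Day 0 mark would not capture it.

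**5. Stopping rule**

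- No Visit 2: 30 days after Visit 2 has no starting date, so only resolution remains as an end point.
- With a Visit 2: Section 7.0 stops at the earlier of resolution and 30 days, while Section 7.2.1 continues recording until resolution. An event unresolved at 30 days is treated differently by the two sections.

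Copying Section 7.0 into footnote H would correct the scope but neither of these two problems.

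**The case against.** The best defence is that Section 7 is explicit twice, and that Section 7.2.1 is headed as the recording duties of the sites. A careful site would follow it over a calendar footnote. That is plausible, but nothing in the documents makes Section 7 prevail, and complete recording should not depend on which page staff consult.

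The second argument is that little harm is likely, and much of this stands. The PET images yttrium-90 already implanted, with no added tracer (Section 1.1), and a low-dose CT (Appendix II). The contrast example applies only to a subset of unstated size, so neither 33 nor 43 is its denominator. Attribution will often be uncertain, because a chemistry change after radioembolization may come from the treatment. The counts describe patients under a rule, not events lost.

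It also stands that not every later contact falls under the footnote. Section 5.0 allows the 1-month visit on the day of a second treatment. That day is also a Visit 1, whose adverse event mark has no footnote.

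A reader might infer more than the documents support:

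- *That safety reporting fails.* Section 7.2.2 sends scan-related SAEs to the Study Monitor within 24 hours. For the local IRB it says "Each investigator is responsible to report all AEs/SAEs that are possibly, probably or definitely related to the investigational PET CT scans performed". On doubtful cases, "Any investigator who is in doubt of whether a particular AE needs to be reported is directed to call the Study Monitor". None of this is tied to Visit 2.
- *That the side-effect analysis is damaged.* Section 8.0 relates side effects to radiation dose in healthy tissue. Footnote H and Section 7.0 are both confined to scan-related events, so changing one to match the other does not alter that analysis.
- *That about 33 patients have no adverse event recording at all.* The Visit 1 assessment is unrestricted; the gap concerns follow-up.

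**Conclusion.** This is an internal inconsistency in an operative rule, and footnote H is the text that is wrong. It leaves out the Day 0 scan, which is planned for all 43 patients, and at follow-up it gives roughly 33 of them (77%, on the anticipated 10 Day 1 patients) nothing to record.

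The consequence is modest: possible under-recording on the CRF of scan-related events, mainly non-serious ones, first found at follow-up. How many cannot be estimated, because the documents give neither an event rate nor the size of the contrast-CT subset. The conclusion assumes that a site follows the footnote as written. It does not depend on the exact number of Visit 2 patients. The correction should be made, because it costs almost nothing and restores the scope that the sponsor set in Section 7.

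**What to change.** 1. In footnote H, replace the reference to the Day 1 scan alone with the Visit 1 and Visit 2 PET-CT scans, as in Section 7.0.
2. As a clarification, state that this includes the contrast CT done with the Day 0 PET-CT and the scans after a second radioembolization. Sections 7.0 and 7.2.1 name neither, so this settles the scope and does not merely repeat it.
3. In footnote H and Section 7.0, replace the 30 days counted from Visit 2 with a rule that works for every patient, for example resolution or 30 days after the last protocol PET-CT, whichever is earlier. Align the until-resolution wording of Section 7.2.1 with it.

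The cost is a few phrases and slightly more CRF recording. No visit, procedure, sample size or analysis changes. There is one trade-off: a 30-day cap would shorten follow-up of unresolved events compared with Section 7.2.1. If the sponsor does not want that, following events to resolution avoids it, and Section 7.0 would then need to drop its cap.
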